### **4. CMIR client (patient) level mechanisms**

**CSC services.** These data will be collected from the CSC with signed, written consent of the parent, and assent for those adolescents under age 18.

**Other non-CSC services.** *The Child and Adolescent Services Assessment* [CASA] is a parent-report instrument designed to assess at follow-up the use of mental health services for youth across 31 settings including inpatient, outpatient, and informal services. The measure has acceptable psychometric properties. Collateral information on treatment attendance (attendance at first treatment appointment and total number of treatment sessions attended) will also be collected by contacting each juveniles’ treatment provider at the 3-month follow-up. A release of information is requested at baseline, for both primary care physicians (PCP) and their mental health provider/agency, as part of the court intake process. The consent form will also contain language allowing the research team to collect this information from the youth’s treatment providers.

**Treatment motivation (self-report and parent/caregiver report).** The *Motivation for Youth’s Treatment Scale*, an 8-item measure, will be used to assess the youth’s motivation to engage in treatment at baseline and at follow-up. The total scale and two subscales (Problem Recognition and the Treatment Readiness) produce alpha coefficients of above .80.

**Barriers to treatment.** *The Barriers to Treatment Participation Scale*, a 44-item measure, will be completed at baseline and 3-month follow-up by caregivers to assess barriers that parents/caregivers experienced since intervention and the role those barriers may play in treatment engagement. Alpha coefficients range from 0.61 to 0.80.

**Treatment satisfaction** information will be gathered as part of the follow-up qualitative interview. Youth and caregivers will be interviewed about their satisfaction with the Enhanced Referral process as well as treatment at the 3-month follow-up.

### **5. CMIR client (patient) level outcomes**

**General psychopathology.** The Brief Problem Monitor (BPM) will be completed at baseline and 3 month follow-up by youth and caretakers to assess general psychopathology including items for rating Internalizing (INT), Attention (ATT), and Externalizing (EXT) problems. The items are drawn from the *Youth Self Report* (YSR) and the *Child Behavior Checklist for Ages 6-18 (CBCL63/6-18)*. The reliability and validity of these measures have been documented. Each item is rated 0 = not true, 1 = somewhat true, or 2 = very true. The BPM was chosen because it assesses behavior over various time periods whereas the CBCL/YSR are designed to assess behavior over a 6-month period.

The *Mini International Neuropsychiatric Interview for Children and Adolescents* (MINI-KID) is a structured diagnostic interview used to characterize adolescents' past and current psychiatric diagnoses and can be completed in 20-30 minutes. Parents of adolescent participants will complete a collateral assessment of their child's past and current psychiatric diagnoses using the MINI-Kid-P collateral interview. Psychometric properties are acceptable and results in reliable and valid psychiatric diagnoses for children and adolescents.

**Psychotic symptoms.** The *Structured Interview for Psychosis-risk Syndromes* (SIPS) is a semi-structured interview targeting interviewees' experiences of attenuated symptoms and other indicators of psychosis risk. The SIPS takes approximately 45-90 minutes to complete and assesses the presence of positive, negative, disorganized, and general symptoms. Respondents are determined to meet criteria for psychosis-spectrum disorders/syndromes based on their endorsement and description of five positive symptoms including odd or delusional thoughts, paranoia/suspiciousness, grandiosity, perceptual abnormalities, and disorganized communication. Factors such as the frequency and intensity of positive symptoms, along with the level of conviction (belief that the experience is real) and interference (i.e. associated distress or impairment), are used to determine whether individuals meet criteria for full-threshold psychosis or any of three risk syndromes. The SIPS is the most widely-used psychosis-risk assessment in North America; it has been used to identify individuals with significantly elevated risk for psychosis. Additionally, the SIPS is designed to consider comorbid disorders that may better account for symptoms that could, in isolation, be conceptualized as psychosis-spectrum. The MINI will be completed prior to the SIPS so that comorbid diagnoses will be available. Elevations on the symptom scales of the BPM will also be available and will inform specific SIPS prompts to help with differential diagnosis considerations. In addition, in order to ensure collection of reliable and valid data from the SIPS, Co-I [name] will audiotape interviews, with participant permission, and she will present the case to two of the Investigators on the study. Differential diagnoses will be discussed as well as whether symptoms might be better explained by other disorders.

In addition to rating current symptomatology at the date of interview, the SIPS is designed to track the emergence and progression of symptoms over time. For all positive symptoms that meet either risk or psychosis threshold, a timeline is established to retrospectively track when symptoms first reached clinical significance and the date when respondents would have first met risk or psychosis criteria. The SIPS is also designed to track symptom progression across assessment time points. At each assessment, the rater determines whether individuals meeting psychosis/risk criteria are best characterized as having progressing (i.e. worsening), persisting (i.e. stable), or remitting (i.e. partially or fully remitting) illness. This onset and trajectory information will be used to define the start of illness as well as to measure DUI and DUP.

**Duration of Untreated Illness (DUI).** DUI (including DUP) is defined as the time between the onset of symptoms and the initiation of adequate treatment. DUI will be measured using a combination of measures, specifically the SIPS to track positive symptom onset, the CASA to track adequate treatment, and a summary measure to calculate both DUI and DUP. Given that many DUP measures exist, no particular tools stand out as superior, and the specific tool used to measure DUP does not seem to have a significant impact on mean or median DUP, we will derive DUP in conjunction with established measures of symptoms and treatment. Using a validated measure of psychosis-spectrum symptoms, namely the SIPS, we will be able to create a thorough timeline of symptom onset and progression. Given the lack of consensus in the literature surrounding what constitutes adequate or effective treatment across psychosis and risk populations, two reasonable treatment variables will be included in the measurement of DUI and DUP: 1) date of first completed course of antipsychotics for one month or more, or 2) date of initiation of consistent psychosocial treatment (attending 4 or more sessions within 6 weeks), including psychosis-specific symptom monitoring and/or intervention. Both of these variables will be captured by follow-up questions on items contained on the CASA, and the earlier of the two dates will be considered the date of adequate treatment provision. We will synthesize SIPS and treatment date in order to calculate DUP and DUI. The DUI summary form will be reviewed with parents to determine if the onset of psychosis symptoms aligns with their perspective of when symptoms emerged (to help account for lack of insight that may interfere with accurate reporting from youth), and clinical judgment will be used to navigate discrepancies and determine approximate DUI/DUP in the consensus meeting.

**Functioning.** *Global Functioning- Role and Social Scales* (GF-R and GF-S) are clinician rated scales measuring functioning across two domains: role fulfillment and social integration/engagement. This set of scales was developed for the North American Prodrome Longitudinal Study (NAPLS), a large multisite study investigating psychosis-risk, as a way to obtain consistent ratings across study sites. The measure was designed for individuals in the age range of highest risk for psychosis (i.e., ages 12-29), and it includes detailed

rating anchors based on developmentally appropriate activities and difficulties that may emerge in early stages of psychosis. Each GF scale includes 10 categories of functioning rated 1-10, with lower scores indicating more impairment. In addition to rating an individual's current level of functioning, the GF scales include ratings of the individual's highest and lowest rating within the past year (rated on the same scale, 1 to 10) to track changes in functioning across time. The GF scales are rated using information gathered through clinical evaluation (e.g., SIPS and MINI). In a recent study comparing the GF scales to similar functioning scales among help-seeking young people, Wilson and colleagues (2014) reported moderate to strong correlations between the measures. In addition to establishing adequate concurrent validity, this study looked at depression in relation to the GF scales and results suggested that the GF scales may successfully separate functioning from psychiatric symptom severity. This possibility, in addition to the brief and easily scored format of the GF scales, made the GF-R and GF-S appealing options for the current study.

**Recidivism** (collateral data from RIFC database). *Juveniles' recidivism rates* (e.g., new arrests), *description of related charges* (e.g., substance-related, property) and *time detained/incarcerated* (all tracked by the RIFC database) will be available.

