**Fidelity to the Enhanced Referral/Linkage to Care condition.** We will have the CSC clinician, who will be employed by the research project but also work at the CSC, audiotape their conversation with the family in the enhanced referral phase of the study. The CSC clinician will use a hand-held audio recorder so that only the CSC clinician's portion of the conversation will be recorded. Fidelity will also be rated by interviewing the parent/caregiver at the baseline research assessment, which will typically occur within a week of the JID

appointment. Caregivers will be asked what the CSC intake worker said to them about scheduling a CSC appointment. The RA conducting the assessment will record verbatim the parent's responses. In both the clinician reported and parent reported data collection, fidelity will be rated by PI [name] and Co-Is [name] and [name] on a two-point scale (0= not satisfactory; 1= satisfactory). If there is disagreement, a consensus meeting will be held to resolve discrepancies in ratings.

**Baseline and follow-up assessment.** Families in both phases of the study will complete the same assessments at baseline and 3-month follow-up to gather data on treatment history, psychosis-spectrum symptoms, general psychiatric symptoms and functioning, as well as JJS contacts (see details below under Measures). In addition, at follow-up, we will interview families about barriers to treatment linkage and treatment satisfaction. The RA and Co-I [name] will be blind as to whether the families were seen for follow-up CSC or mental health care until after the interviews are completed.

We will also interview JID intake workers and CSC staff to assess both services and implementation factors related to referral process and completion. The baseline and follow-up assessment battery were designed to minimize participant burden and to thoroughly assess psychosis-spectrum symptoms. The follow-up assessment will be scheduled 3-months post-referral to the CSC. The 3-month follow-up period will allow us to assess whether high risk youth engage in treatment with the CSC or other mental

healthcare. Both baseline and follow up interviews will be conducted in-person and last approximately 1.5- 2 hours.

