Co-I [name] will administer the Structured Interview for Psychosis-risk Syndromes (SIPS), described below. She has received formal training and certification by SIPS developers to conduct the interviews, and she was trained to research quality reliability (ICC>.8) within her prior research team. She will administer all the SIPS interviews in order to maintain consistency across the two phases of the study as well as across participants. At baseline, when we will assess youth with both positive and negative screens, Co-I [name] will be "blind" to whether youth have screened positive or negative. At follow-up, she will know that all youth have screened positive on the MAYSI-2 and *PQ-B*, but the RA and Co-I [name] will instruct families not to disclose whether they followed through with the referral to the CSC or whether they have received any type of follow-up mental health care until after the assessment is completed.

**Training in assessment.** Training in the assessment protocol will occur during the first 2 months by Co-I [name], following procedures we used in other RCTs. Under Co-I [name]'s oversight, research staff conducting baseline assessments will also receive training on working in the JJS and on how to appropriately respond to logistical questions that participants' may have about the JJS. Co-I [name] will oversee the baseline assessment and Co-I [name] will oversee the follow-up assessment component of the protocol. If parents request it, the results of the evaluation will be shared with the CSC in both phases of the study.

**Procedures for mental health deterioration/safety concerns.** It is possible that some participants will report symptoms during their research assessment that may warrant additional mental health care. If any youth indicates serious psychotic symptoms or suicidal/homicidal thoughts, a safety plan will be established by Co-[name]. Either [name], [name], [name], or [name] all licensed clinical psychologists, will be notified and review the safety plan. In all cases, if families are in treatment at the CSC, or a mental health clinic, a mutually agreeable plan will be derived with the CSC clinical team. In the event of an acute crisis, patient will be transferred to the Rhode Island Hospital (RIH) psychiatric Emergency Department, where all the PI and Co-Investigators [name] and [name] have staff appointments and clinical privileges (See **Human Subjects**).

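### Masking to follow-up care ends with the interview, and nothing fixes the symptom-onset date before the consensus meeting settles DUI/DUP with treatment dates to hand

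*Combined protocol and SAP*

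**What the plan says.** **Onset.** The SIPS paragraphs of Measures, section 5, say that for symptoms at risk or psychosis threshold "a timeline is established to retrospectively track when symptoms first reached clinical significance", along with the date on which criteria would first have been met.

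**Treatment date.** The DUI paragraph defines two qualifying treatments, an antipsychotic course of a month or more and psychosocial care of four or more sessions within six weeks. Both are captured by follow-up questions on the CASA, and "the earlier of the two dates will be considered the date of adequate treatment provision".

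**Combination.** The same paragraph says: "We will synthesize SIPS and treatment date in order to calculate DUP and DUI". The DUI summary form is then checked with parents against their own view of when symptoms began. Where accounts differ, "clinical judgment will be used to navigate discrepancies and determine approximate DUI/DUP in the consensus meeting".

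**Masking.** Under Baseline and follow-up assessment, the RA and the SIPS interviewer "will be blind as to whether the families were seen for follow-up CSC or mental health care until after the interviews are completed". At follow-up they "will instruct families not to disclose whether they followed through with the referral to the CSC", or whether they received other mental health care, until the assessment is over. At baseline the SIPS interviewer is blind "to whether youth have screened positive or negative". No masking is stated for the consensus meeting, and none to study phase.

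**The concern.** DUI and DUP are differences between two dates. The treatment end follows a written rule. The onset end is retrospective, comes from two informants, and the Background section itself describes onset as often insidious. When the two accounts disagree, judgment decides. If the people deciding already know whether and when the youth reached care, that knowledge can pull the onset date in either direction, and the shift passes in full into the duration.

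The Specific Aims (3A) and the Aim 3B analysis text both plan to examine effects of the intervention on DUP, and Aim 3B adds DUI. Aim 3C, as titled, relates treatment linkage and attendance to DUP. In each case the exposure is linkage or is meant to change it. A judge who knows linkage while dating onset could therefore create or hide part of the association under study. The Significance section offers blinding of assessors as part of the study's rigor, but the last step in deriving this outcome lies outside that blinding.

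**Working it through.** The plan gives no figure to reproduce here, so the main check is to follow the sequence of steps and see where masking applies.

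1. **Baseline SIPS.** Onset is dated by the structured timeline. Masking is to screen result only. The Fidelity paragraph says the baseline assessment typically falls within a week of the intake appointment.
2. **Follow-up SIPS, three months after referral.** The timeline is available again. The interviewer and RA are masked to follow-up care.
3. **Interviews end.** The masking lapses under its own terms.
4. **Treatment dates.** These come from the CASA, which the plan describes as a follow-up instrument, and from CSC records.
5. **Synthesis and parent review.** Onset and treatment information are brought together, and parents are asked about onset.
6. **Consensus meeting.** Judgment resolves discrepancies and fixes the approximate DUI/DUP.

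Two links in this chain are inferred. The plan does not say outright that the meeting sees treatment dates while settling onset, but a duration cannot be determined without them, and the synthesis is described before the meeting. Nor does it define who attends. The SIPS paragraph describes the interviewer presenting cases to two investigators, and the fidelity paragraph describes a separate consensus meeting about fidelity ratings.

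**How a shift passes through.** Let T be the treatment date, O the onset date and D = T − O. Moving O later by s months changes D by −s. If this happens in a share f of a group, the group mean changes by f × s. The documents give neither f nor s, so the bias cannot be computed.

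**A sense of scale (illustration only).** The assumptions are:
- Phase I linkage of 48–62%, using the usual community uptake quoted in Background as a stand-in.
- Phase II linkage of 80%, from the Aim 2A analysis text.
- The same linkage among youth who have a DUI/DUP.
- Duration in untreated youth counted to the follow-up visit.
- The full three months gained by each additional linked youth.

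The mean reduction from additional linkage is then:
- (0.80 − 0.62) × 3 = 0.54 months
- (0.80 − 0.48) × 3 = 0.96 months

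Now suppose that knowing a youth linked moves onset by an average of s months, equally in both phases. The false phase difference is s × (0.80 − p), where p is Phase I linkage:

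| s (months) | p = 0.62 | p = 0.48 |
|---|---|---|
| 1 | 0.18 | 0.32 |
| 2 | 0.36 | 0.64 |
| 3 | 0.54 | 0.96 |

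The ratio to the benchmark is s/3 whatever p is. No knowledge of phase is needed; knowledge of linkage is enough. The benchmark is rough. It ignores faster linkage among youth who would have linked anyway, and it credits the full three months although treatment cannot start on the day of referral.

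**The case against.** The strongest reply is that onset is not freshly chosen by people who know the outcome. The SIPS timeline dates it first, in an interview masked to follow-up care. The same assessments are done at baseline, typically within a week of intake, whereas CSC evaluations are typically scheduled within two weeks and psychosocial care counts only with four or more sessions within six weeks. For most youth not already in care, an onset record should therefore exist before any treatment date the study could produce. Judgment then handles discrepancies only. All of this stands, and it narrows the point. It does not close it, because the plan does not say the baseline onset date is locked, and the consensus step may revise it. About 26% of youth presenting at intake report being already in treatment, and for them the baseline record need not precede the treatment date.

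A second reply is that this is a pilot which disclaims effect estimation. Its key parameters are the SD of the SIPS positive symptom scores, their pre-post correlation and R². DUI/DUP is not among them, and the Aim 1 summaries of mean, median and range make no phase contrast. That also stands and limits the stakes. The Aim 3C analysis text names only SIPS and BPM symptom change, although the aim's title names DUP. Even so, effects on DUP and DUI are stated objects of examination.

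A reader might go further and infer that there is no masking to treatment at all, or that judgment sets every onset date. The documents contradict both. A reader might also ask that the meeting be masked to phase. None is stated, but the phases are consecutive calendar blocks in an open design, and of the SIPS interviewer the plan says "She will administer all the SIPS interviews in order to maintain consistency across the two phases of the study". Masking to phase is impractical and is not asked for.

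**Conclusion.** The point holds in a limited form. Masking to follow-up care covers the interviews and stops there. The later step that settles onset discrepancies and DUI/DUP is unmasked as written, and no order of steps protects the onset date. That the meeting has treatment dates in view is a strong inference rather than a stated fact.

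Bias is possible, not shown. Its direction is unknown and its size cannot be derived from the documents, so no percentage should be attached to it. The illustration shows only that, under its assumptions, an average shift of one to three months in linked youth would be one third to all of the mean reduction expected from additional linkage. A reader might infer that the pilot's main results are compromised; the documents do not support that, because the parameters intended to size the definitive trial do not depend on DUI/DUP. The case for acting is that the better procedure is cheap and that a loose derivation could carry over into the later trial.

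**What to change.** In the DUI paragraph, split the summary form into two parts and fix their order.

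1. Reconcile the SIPS and parent accounts of onset, using the baseline SIPS where possible. Record the final risk-onset and psychosis-onset dates in REDCap before CASA or CSC treatment dates are opened. Clinical judgment is confined to this step.
2. Open the treatment dates and apply the rule already stated, the earlier of the two qualifying dates.
3. Compute DUI and DUP by subtraction, with no further adjustment.
4. Keep the unreconciled youth and parent onset dates, and repeat the DUI/DUP summaries and any phase or linkage comparison with each as a sensitivity analysis.

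State also who attends the consensus meeting.

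The same people and data are used. The costs are a revised form, a changed order of review with parents, and the loss of treatment history as a memory anchor at the consensus step. Some exposure remains: parents know what care was received, and treatment already under way at intake may be known from baseline. The change removes the judges' discretion once treatment dates are open, not every source of influence.
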